#### Transition to TIW for all subjects randomized to vadadustat:

All subjects randomized to vadadustat (Main study and ESA hyporesponder parallel study), who complete the 12-week once daily dosing regimen and who meet all the Week 12 transition criteria for switching from daily to TIW dosing, will initiate TIW dosing at a starting dose one tablet greater (+150 mg) than the final dose in the daily dosing.

---

**Note:** Subjects who are not eligible to switch from daily vadadustat to TIW dosing at Week 12 will remain on daily dosing for the remainder of the study.

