## 8.2 Analysis Population

The following analysis populations will be used in this study:

- Randomized population: defined as all randomized subjects. Analyses of this population will be based on the randomized treatment.
- Full Analysis Population (FAS): all subjects in the randomized population who received at least one dose of study drug and had at least one Hb assessment during the primary efficacy evaluation period. Analyses of this population will be based on the randomized treatment.
- Safety Population: all subjects in the randomized population who received at least one dose of study treatment. Analysis of this population will be based on the actual treatment received. Subjects who received in error some vadadustat and some epoetin alfa will be classified by the more frequently received drug.
- Per protocol (PP) population: all randomized subjects who received study drug during the primary evaluation period, had at least one Hb assessment during the primary efficacy evaluation period, received no rescue therapy (with ESA or transfusion) prior to the evaluation period, and had no major protocol deviation affecting the primary endpoint analyses. Major protocol deviations leading to exclusion from the PP population will be specified prior to database lock on a blinded basis and recorded in a separate document. Analyses of this population will be based on actual treatment received.
- Pharmacokinetic (PK) population: will include all randomized subjects who received study medication (vadadustat or EPO) and had enough drug concentrations to estimate AUC and Cmax. Analysis of this population will be based on the dose amount taken at the date of PK sampling for vadadustat group.

Efficacy analyses will utilize the Randomized, FAS, and PP Populations while safety analyses will utilize the Safety Population. PK analyses will utilize the PK Population. However, if the population size of FAS and PP is  $\geq 95\%$  of the size of randomized population, no additional summary table will be presented for FAS and PP populations.

---

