### 9.3 Other Secondary Endpoints

- Intravenous (IV) iron supplementation and oral iron

The average weekly elemental iron use during the treatment period which is defined as first dose date to last dose date + 7 days will be calculated for weekly intervals from both oral and IV iron medications (Oral iron dose will be converted to elemental iron dose; the list will come from the medical team.). The treatment period will be divided in periods of 7 days and for each of these periods the weekly mean of IV iron will be used using the following formula:

$$\text{Weekly iron use for each subject} = \text{Total iron in mg} / [(\text{last dose date} + 7 - \text{first dose date} + 1) / 7]$$

The average weekly iron use will be summarized by treatment group using descriptive statistics. The content of elemental iron for different kinds of IV iron is presented in [Appendix 5](#).

In addition, numbers and percentages of subjects with at least one administration of elemental iron will be summarized by treatment group.

- ESA administration and RBC transfusion

ESA medication will be considered as rescue if the ESA medication was taken between the first dose date to the last dose date + 7 days and the reasons for the ESA medication use is checked as confirmed Hb  $< 8.5$  g/dL on the CRF and the ESA medication wasn't taken during the period of Eurofins ransomware attack (after Jun 20, 2019 and before July 9, 2019).

---

Epoetin alfa dose will be administered based on the subject's central laboratory Hb value and the approved epoetin alfa US PI for adult patients with CKD on dialysis. From Baseline/Day 1 to Week 20, dose will be adjusted to achieve and maintain Hb levels within the target range of 10.0 and 11.0 g/dL, inclusive. Because epoetin alfa is titratable, increase in dose is not considered rescue unless the investigator specifically designates it as such; however, increases in dose relative to last dose will be characterized in three categories by percentage increase: <50%, ≥50% and <100%, and ≥100%. In addition to the investigator's judgement of rescue, the increase in dose ≥50% or ≥100% will be considered as additional conditions for ESA rescue in EPO group.

RBC transfusion will be considered as rescue if the RBC transfusion was taken between the first dose date to the last dose date + 7 days and the reasons for the RBC transfusion is checked as Worsening Anemia due to CKD on the CRF.

[figure not shown]

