The study will consider the following efficacy endpoints related to ESA administration and RBC transfusion.

- Receipt of any ESA administration
- Receipt of any ESA administration or dose with at least 50% increase for the EPO group
- Receipt of any ESA administration or dose with at least 100% increase for the EPO group
- Receipt of ESA administration as rescue
- Receipt of ESA administration as rescue or dose with at least 50% increase for the EPO group
- Receipt of ESA administration as rescue or dose with at least 100% increase for the EPO group
- Receipt of any RBC transfusion
- Receipt of RBC transfusion as rescue

Number of subjects received ESA administration (any or rescue) and RBC transfusion (any or rescue) will be summarized by treatment group and time period. The following time periods will be summarizing:

- Baseline visit (inclusive) to week 12 (inclusive)
- Week 12 (exclusive) to week 20 (inclusive)
- Baseline visit (inclusive) to week 20 (inclusive)

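### The ESA-rescue count drops events that meet the plan's own Hb criterion, the per-protocol rescue exclusion stops before Weeks 10 to 12, and two statements on epoetin dose increases conflict

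*SAP*

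**What the plan says.** Section 9.3 counts ESA as rescue when three conditions hold together: it falls between first dose and 7 days after last dose; "the reasons for the ESA medication use is checked as confirmed Hb" below 8.5 g/dL; and it was not "taken during the period of Eurofins ransomware attack (after Jun 20, 2019 and before July 9, 2019".

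Transfusion is rescue if the "RBC transfusion was taken between the first dose date to the last dose date + 7 days" and the CRF reason is worsening anaemia due to CKD. No calendar clause is attached.

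For epoetin, the same section says that an "increase in dose is not considered rescue unless the investigator specifically designates it as such". It then says that increases of at least 50% or at least 100% "will be considered as additional conditions for ESA rescue in EPO group". The endpoint list that follows gives ESA rescue a line of its own and adds separate lines such as "Receipt of ESA administration as rescue or dose with at least 50% increase for the EPO group".

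The PP definition in Section 8.2 requires that the subject "received no rescue therapy (with ESA or transfusion) prior to the evaluation period". Section 6 averages all Hb values in an analysis period, and Section 9 uses observed data for every Hb endpoint. Section 4 reports no change in planned analyses and, on the attack, names only an Hb sensitivity analysis.

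**The concern.** ESA rescue is a listed secondary endpoint, and rescue is also one of the PP filters. The study is descriptive, with no inferential modelling, so the tabulated counts and means are the result and the definitions carry the weight.

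Three things need attention:

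1. A calendar clause deletes events that the plan otherwise calls rescue.
2. PP, the only efficacy set with a rescue filter, leaves that filter open during the weeks in which the primary endpoint is measured.
3. The rescue status of an epoetin dose increase depends on which sentence of Section 9.3 the programmer follows.

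**Working it through.** The SAP gives no rescue rate or effect size, so there is no stated figure to reproduce. The check is a logical reading plus date arithmetic.

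**What the date clause removes.** ESA given for any reason other than confirmed Hb below 8.5 g/dL already fails the reason condition. The only events left for the date clause to act on are those coded with that reason.

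**Length of the clause.** After 20 June and before 9 July 2019 means 21 June to 8 July: 10 days in June + 8 in July = 18 days.

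**Share of the rescue window.** With a last dose on Day 141 (the Week 20 target in SAP Table 1), the window ends on Day 141 + 7 = Day 148. Then 18/148 = 12.2%, for a subject on study throughout the attack.

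**Illustrative undercount.** Let p be the true proportion rescued with ESA and f the share of an arm on study through the whole window. Assume one rescue per rescued subject and rescue spread evenly over time. The undercount is p × f × 18/148. None of these inputs is in the SAP.

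| p | f | Undercount (percentage points) |
|---|---|---|
| 5% | 10% | 0.06 |
| 20% | 50% | 1.2 (20.0% reported as 18.8%) |
| 30% | 100% | 3.65 |

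If rescue clustered in the window, the loss would be larger.

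**Consistency with neighbouring rules.** In the same 18 days, a transfusion can count as rescue and an epoetin increase of 50% or more can satisfy the added epoetin condition. ESA given to a vadadustat subject for confirmed Hb below 8.5 g/dL cannot count.

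**Disclosure.** Section 1 bases the SAP on a protocol version dated 5 April 2019, before the attack, so the clause cannot come from that version. Neither Section 4 nor the revision history mentions it; both refer to the attack only for Hb data.

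**PP gap.** Table 1 places Weeks 10 to 12 on Days 64 to 88, which is 88 − 64 + 1 = 25 days, or 25/88 = 28% of the first 88 days. A subject given ESA or blood on those days can remain in PP if study drug was received in the period and no major deviation affecting the primary endpoint was recorded. The Hb values after rescue then enter the period average. The same values enter the Randomized and FAS analyses, since no censoring after rescue is stated.

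**Which definition PP uses.** Section 8.2 does not say whether the Section 9.3 definition of rescue applies. If it does, a subject given ESA for low Hb in the attack window before Week 10 also stays in PP.

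**Dose increases.** One sentence makes investigator designation the only route by which an epoetin increase becomes rescue. The next makes the size of the increase a route as well, in the epoetin group only. Both cannot define the same endpoint.

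**The case against.** **The date clause may have a reason, and other lines still catch the events.** The SAP does not say how Hb was confirmed while the laboratory was affected, so the coded reason may have been doubtful. The clause is not worded by arm, in-window ESA still counts in the any-ESA line, and in-window transfusion rescue still counts. Section 9.5 also removes vadadustat subjects randomized before 23 July 2019 from a primary-endpoint sensitivity analysis, which takes out every vadadustat subject given ESA in the window. This stands in part. But any ESA ignores the reason for use and epoetin is the comparator's study drug, so that line is only a partial substitute. The Section 9.5 analysis concerns Hb and does not repair the rescue count.

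**A reader might infer that the rules as a whole lean towards vadadustat.** The documents do not support that. The PP wording is the same for both arms. Plain ESA rescue is reported separately from the epoetin-only lines, and there any lean could run the other way. If the 50% condition fed PP, it would remove poorly controlled epoetin subjects, which could favour epoetin.

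**A reader might infer that the PP gap inflates the vadadustat mean.** Its sign depends on the comparison. Against the Hb a subject would have had without rescue, rescue raises the mean. Against excluding the subject, it may lower it: starting below 8.5 g/dL with an assumed lift of 1 g/dL, the subject reaches at most about 9.5. If the others average an assumed 10.5, keeping 5% such subjects shifts mean Hb by 0.05 × (9.5 − 10.5) = −0.05 g/dL. Baseline values matter too, because the endpoint is a change. No size or direction can be claimed.

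**A reader might also argue that vadadustat tablet steps are uncounted equivalents of a 50% epoetin rise.** The step of "one tablet greater (+150 mg") in Section 3.3 is the daily-to-TIW transition, where the weekly amount falls (for example 7 × 300 = 2,100 mg to 3 × 450 = 1,350 mg). The SAP states no Hb titration step for vadadustat, and Section 8.9 tabulates Hb-based dose increases for each treatment group.

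**Conclusion.** The point holds as three definitional faults, without a claim that they favour one arm. The date clause removes from rescue only events that meet the plan's Hb criterion. It is undeclared, has no counterpart in the neighbouring rules, and no analysis without it is planned. PP leaves rescue during Weeks 10 to 12 unfiltered. The two statements on epoetin increases must be reconciled.

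The size is modest and mostly unknown. The 12.2% rests on a Day 141 last dose and presence throughout the attack. The undercount of 0.06 to 3.65 percentage points rests wholly on the assumed p, f and even spread. The PP effect has no determinable sign. The SAP does not show when or why the clause was added, so no motive should be inferred. These are corrections that should be made; in an exploratory, descriptive study they do not undermine the trial.

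**What to change.** Change counting rules only; no treatment rule is affected.

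1. In Section 9.3, report ESA rescue in both arms without the date clause as the main count and with it as a sensitivity count. Declare the clause in Section 4.
2. In Section 8.2, state which rescue definition PP uses, do not apply the date clause to it, and extend the exclusion to rescue before or during Weeks 10 to 12.
3. In Section 9.5, add a sensitivity analysis of the primary endpoint that omits Hb values after rescue, in both arms.
4. Reconcile the two Section 9.3 statements on epoetin increases. Label the 50% and 100% lines as epoetin-only supportive summaries that define rescue neither for between-arm comparison nor for PP.

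The cost is SAP wording and a small amount of programming. PP may shrink slightly and rescue counts may rise. Section 8.2 drops the extra FAS and PP tables when those sets are at least 95% of the randomized set, so a smaller PP set could mean that PP tables must be produced.

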## 9.4 Exploratory Endpoints

#### **9.4.1 Health-related quality of life (HRQOL) measure 36-Item Short-Form General Health Survey (SF-36v2)**

The Medical Outcomes Study 36-Item Short-Form Health Survey (SF-36v2) is a multi-purpose, short-form health survey with 36 questions (see [appendix 1](#)). It yields an 8-scale profile of functional health and well-being scores as well as psychometrically-based physical and mental health summary measures. It is a generic measure, as opposed to one that targets a specific age, disease, or treatment group. Accordingly, the SF-36 has proven useful in surveys of general and specific populations, comparing the relative burden of diseases, and in differentiating the health benefits produced by a wide range of different treatments.

The SF-36 contains 36 items that measure eight dimensions: (1) physical functioning (PF); (2) role limitations due to physical health problems (RP); (3) bodily pain (BP); (4) social functioning (SF); (5) general health perceptions (GH); (6) role limitations due to emotional problems (RE); (7) vitality, energy or fatigue (VT); and (8) mental health (MH).

The SF-36v2 will be scored for the 8 domains according to the standard SF-36v2 scoring algorithms (0 to 100 scales) explained in the SF-36v2 Manual and Interpretation Guide ([Ware et al., 1993](#)). The PCS and MCS will be scored according to the standard SF-36v2 scoring algorithm (0 to 100 scales) explained in the SF-36v2 Physical and Mental Health Summary Scales Manual ([Ware et al., 1994](#)).

Each of these 8 domains is consisted of several questions. Table 1 and Appendix 1 describe the individual item for each domain.

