**Table 2 Transformation of SF-36 items to a scale from 0 to 100**

| Question # (Appendix 2)                              | Self-perceived health |              |
|--|-----------------------|--------------|
|  | 0 (Poor)              | 100 (Better) |
| 1, 2, 6, 8, 9a, 9d, 9e, 9h, 11b, 11d                 | 5                     | 1            |
| 3a to 3j   | 1                     | 3            |
| 4a to 4d, 5a to 5c, 9b, 9c, 9f, 9g, 9i, 10, 11a, 11c | 1                     | 5            |
| 7  | 6                     | 1            |

Programming note: Once transformed – the items should each span the range 0 to 100.

Item scores for each dimension are coded, summed, and transformed to a scale from 0 to 100, with higher scores indicating better self-perceived health (See detail in [Appendix 1](#) and [Appendix 2](#)). The calculation of the normalized domain scores relative to the original item response is presented in [Appendix 3](#). The score for each domain ranges from 0 to 100. In addition to the domain scores described above, standardized and norm-based scores are calculated for each domain. The formulae are given below.

| Domain               | Standardization (Z-score)        | Norm-Based Score |
|----------------------|----------------------------------|------------------|
| Physical functioning | $PF\_Z = (PF-83.29094)/23.75883$ | $50+10*PF\_Z$    |
| Role-physical        | $RP\_Z = (RP-82.50964)/25.52028$ | $50+10*RP\_Z$    |
| Bodily pain          | $BP\_Z = (BP-71.32527)/23.66224$ | $50+10*BP\_Z$    |
| General health       | $GH\_Z = (GH-70.84570)/20.97821$ | $50+10*GH\_Z$    |
| Vitality             | $VT\_Z = (VT-58.31411)/20.01923$ | $50+10*VT\_Z$    |
| Social functioning   | $SF\_Z = (SF-84.30250)/22.91921$ | $50+10*SF\_Z$    |
| Role-emotional       | $RE\_Z = (RE-87.39733)/21.43778$ | $50+10*RE\_Z$    |
| Mental health        | $MH\_Z = (MH-74.98685)/17.75604$ | $50+10*MH\_Z$    |

Note: Standardization is based on the 1998 general United States population.

SF-36 physical and mental component transformed scores are calculated using the conventions described below.

| Score                        | Calculation  |
|------------------------------|--|
| Aggregate Standardized Score |  |
| Physical component           | $AGG\_PHYS = (PF\_Z * 0.42402) + (RP\_Z * 0.35119) + (BP\_Z * 0.31754) + (GH\_Z * 0.24954) + (VT\_Z * 0.02877) + (SF\_Z * -0.00753) + (RE\_Z * -0.19206) + (MH\_Z * -0.22069)$ |

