| Vitality           | Items 9a and 9e | All of the time = 5
Most of the time = 4
Some of the time = 3
A little of the time = 2
None of the time = 1 | 4-20               | $(S-4)/16 \times 100$ |
|                    | Items 9g and 9i | All of the time = 1
Most of the time = 2
Some of the time = 3
A little of the time = 4
None of the time = 5 |                    |                       |
| Social functioning | Item 6          | Not at all = 5
Slightly = 4
Moderately = 3
Quite a bit = 2
Extremely = 1                                    | 2-10               | $(S-2)/8 \times 100$  |
|                    | Item 10         | All of the time = 1
Most of the time = 2
Some of the time = 3
A little of the time = 4
None of the time = 5 |                    |                       |

| Scale          | Item                       | Coding  | Range of Raw Score | Normalized Score*     |
|----------------|----------------------------|---|--------------------|-----------------------|
| Role-emotional | Items 5a to 5c      | All of the time = 1
Most of the time = 2
Some of the time = 3
A little of the time = 4
None of the time = 5 | 3-15               | $(S-3)/12 \times 100$ |
| Mental health  | Items 9b, 9c and 9f | All of the time = 1
Most of the time = 2
Some of the time = 3
A little of the time = 4
None of the time = 5 | 5-25               | $(S-5)/20 \times 100$ |
|                | Items 9d and 9h     | All of the time = 5
Most of the time = 4
Some of the time = 3
A little of the time = 2
None of the time = 1 |                    |                       |

\*S = raw score = sum of item scores after coding

---

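### The SF-36 item table in SAP section 9.4.1 contradicts Appendix 3 on the items of Vitality and Mental Health, and nothing says which list governs

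*SAP*

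**What the plan says.** SAP section 9.4.1 gives three directions for scoring the SF-36v2 domains.

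- The general rule: "The SF-36v2 will be scored for the 8 domains according to the standard SF-36v2 scoring algorithms".
- The items of each domain: "Table 1 and Appendix 1 describe the individual item for each domain". The Table 1 meant is the SF-36 table in 9.4.1, not the visit-window table of the same number in section 6. Appendix 1 is a figure that is not reproduced in the available text.
- The calculation, in the text under the SF-36 Table 2: "The calculation of the normalized domain scores relative to the original item response is presented in" Appendix 3.

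Table 1 gives Vitality as 9a, 9c, 9g, 9i and Mental Health as 9b, 9c, 9d, 9f, 9g.

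Appendix 3 builds Vitality from "Items 9a and 9e" and "Items 9g and 9i", and Mental Health from "Items 9b, 9c and 9f" and "Items 9d and 9h".

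The SF-36 Table 2 sets the direction of every item. Its first row, "1, 2, 6, 8, 9a, 9d, 9e, 9h, 11b, 11d", includes both 9e and 9h.

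**The concern.** The plan holds two incompatible definitions of two domains and has no rule of precedence. Table 1 is the place the text names for domain composition, so a programmer could reasonably take the item lists from it, use Table 2 for item direction, and never compare them with Appendix 3.

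The result would be wrong in substance. In the questionnaire (Appendix 2), 9c asks about low mood, 9e about energy, 9g about feeling worn out and 9h about happiness. Table 1 puts a mood item in Vitality in place of the energy item, and a fatigue item in Mental Health in place of a mood item. Change in energy or fatigue would partly appear as change in mental health, and the reverse.

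Both domains enter PCS and MCS, because each composite formula uses all eight z-scores. The rule for missing items is also affected, since it counts missing answers among the items that make up a domain. A range check would not find the error: the raw ranges (4–20 for Vitality, 5–25 for Mental Health) are the same under either list.

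**Working it through.** **Step 1. Compare the lists.**

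| Domain | SF-36 Table 1 (9.4.1) | Appendix 3 |
|---|---|---|
| Vitality | 9a, **9c**, 9g, 9i | 9a, **9e**, 9g, 9i |
| Mental Health | 9b, 9c, 9d, 9f, **9g** | 9b, 9c, 9d, 9f, **9h** |

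The other six domains agree. Over all eight domains, Table 1 has 35 item slots but 33 distinct items: 9c and 9g occur twice, 9e and 9h not at all. Appendix 3 has 35 slots and 35 distinct items, with only item 2 outside the domains. Table 2 covers all 36 items, so under Table 1 it transforms 9e and 9h for no purpose. The item content in Appendix 2 also fits Appendix 3. On the SAP's own evidence, Table 1 is the faulty list.

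**Step 2. Difference in the domain scores.** Appendix 3 gives VT = (S − 4)/16 × 100 and MH = (S − 5)/20 × 100, where S is the sum of coded items, each coded 1 to 5. Only the swapped items differ, so (Table 1 minus Appendix 3):

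- VT difference = (coded 9c − coded 9e)/16 × 100
- MH difference = (coded 9g − coded 9h)/20 × 100

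One category of disagreement gives 1/16 × 100 = 6.25 on VT or 1/20 × 100 = 5 on MH. The maximum of four categories gives 25 on VT and 20 on MH. If the coded answers agree, the difference is zero.

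**Step 3. Carry through to PCS and MCS**, using the constants in 9.4.1: SDs 20.01923 (VT) and 17.75604 (MH); PCS weights 0.02877 and −0.22069; MCS weights 0.23534 and 0.48581; other domains held fixed.

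- MCS maximum (both differences in the same direction): 10 × (25/20.01923 × 0.23534 + 20/17.75604 × 0.48581) = 10 × (0.2939 + 0.5472) = 8.41
- PCS maximum (differences in opposite directions): 10 × (25/20.01923 × 0.02877 + 20/17.75604 × 0.22069) = 10 × (0.0359 + 0.2486) = 2.845, or 2.8

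Scoring all 5⁴ combinations of answers to 9c, 9e, 9g and 9h under both lists gives the same limits.

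**Step 4. One illustrative visit.** Take answers 3, 4, 5, 2, 4, 4, 2, 2, 2 to items 9a to 9i.

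- VT: Table 1 sum 3 + 5 + 2 + 2 = 12, score 50.0; Appendix 3 sum 3 + 2 + 2 + 2 = 9, score 31.25.
- MH: Table 1 sum 4 + 5 + 4 + 4 + 2 = 19, score 70; Appendix 3 sum 4 + 5 + 4 + 4 + 4 = 21, score 80.
- Table 1 minus Appendix 3: PCS +1.51, MCS −0.53.

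**Step 5. One illustrative change.** Suppose 9a, 9e, 9g and 9i each improve from coded 2 to coded 4 and the mood items stay the same.

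| | VT | MH | PCS | MCS |
|---|---|---|---|---|
| Appendix 3 | 8/16 × 100 = +50 | 0 | +0.7 | +5.9 |
| Table 1 | 6/16 × 100 = +37.5 | 2/20 × 100 = +10 | −0.7 | +7.1 |

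This profile is constructed to show the direction of the error. It is not a forecast of the trial data.

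**The case against.** The strongest reply is that the plan already leads to the right scores. It invokes the standard algorithm and places the domain calculation in Appendix 3, which is coherent and complete with items, coding, ranges and formulas. The sentence about Table 1 only says where the items are described. This stands in part. A reader might infer from Table 1 that Vitality, Mental Health, PCS and MCS are in fact mis-scored, but the document does not show that. The error arises only if the domains are built from Table 1, and the SAP does not reveal which list was programmed. What the reply does not remove is the contradiction: no sentence gives Appendix 3 precedence.

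Second, the 9c in the Vitality row could be a 9e misread from the PDF. That is possible, but it would not explain 9g for 9h in the Mental Health row. If only that cell were wrong, Vitality would be unaffected and the per-subject maxima would be 20 on MH, 10 × 20/17.75604 × 0.48581 = 5.5 on MCS and 10 × 20/17.75604 × 0.22069 = 2.5 on PCS.

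Third, the maxima need opposite extreme answers on the swapped items, and the plan reports mean changes by treatment group, where a constant offset between two items cancels. This stands: the figures are limits for one subject and say nothing about the size of a group effect.

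Fourth, a check for duplicate items, or a comparison with Appendix 3, would expose the fault at once. That is true, but the plan calls for neither.

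Finally, a reader might give the point extra weight by regarding Vitality as the domain most relevant to anaemia. The SAP makes no such statement, and the point does not depend on it.

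**Conclusion.** The point holds as a documentary contradiction with a conditional consequence. SF-36 Table 1 is wrong in two cells by the SAP's own Appendix 3, Table 2 and questionnaire wording. If the domains are built from it, one subject's scores can differ from Appendix 3 by up to 25 on VT, 20 on MH, 8.4 on MCS and 2.8 on PCS, and by nothing where the coded answers to each swapped pair agree.

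This assumes that both cells read in the source as they do in the available text, that each item keeps its direction from Table 2 and Appendix 3, and that the other domains are unchanged. The item lists in Appendix 1 could not be checked.

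The reach is limited. The SF-36 falls under the exploratory endpoints and is summarised descriptively at Weeks 12, 20 and 24, so no primary or secondary result is affected. It is still worth correcting, because four reported scores depend on which list is used.

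**What to change.** In the SF-36 Table 1 of section 9.4.1, change the Vitality row to 9a, 9e, 9g, 9i and the Mental Health row to 9b, 9c, 9d, 9f, 9h. Add one sentence to 9.4.1 stating that Appendix 3 governs the composition of the domains. Confirm that the Appendix 1 figure shows the same lists, and that any scoring program already written uses the Appendix 3 items, including in the missing-item rule.

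The cost is two table cells, one sentence and a short program check. No data collection or other analysis changes, and there is no drawback.
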